8.3.4. Measures to Minimise Bias in the Surveys

The following are measures to minimise bias in the surveys:

All questions will be programmed to ensure that questions are asked in the appropriate sequence. Skip patterns will be clearly indicated. Respondents cannot go back to a

question once the question has been answered and cannot skip ahead. All questions must be answered in order to complete the survey. This is important because subsequent questions could provide answers to previous questions, and because all subjects should have the same chance of answering the questions correctly. Other biases are described in the limitation section, however, cannot be minimized by survey design alone.

8.4. Data sources

Parents/carers and referring HCPs of patients enrolled within the registry will be contacted and asked to participate in this study evaluating the effectiveness of risk minimisation measures.

Parent/carers surveys and HCPs surveys will be developed in English and available in translations in the parent/carers' and HCPs' local languages for provision via telephone interviews.

8.5. Study size

All parents/carers and referring HCPs from patients enrolled in the Strimvelis product registry will be invited to complete the surveys. The study will recruit for approximately two years until 10 referring HCPs and 10 parents/carers have completed their respective surveys (length of study may vary contingent upon product uptake).

8.6. Data management

A user-friendly Internet-based survey tool with an intuitive interface will be employed to manage data in this survey. Parents/carers, who have agreed that they may be contacted about such future studies, will be contacted by the Gene Therapy Registry Centre (GTRC). Questions will be asked to the parents/carers and HCPs and responses to the survey entered by the GTRC. Surveys for both parents/carers and HCPs will be entered via an electronic data collection system by the local interviewer.

In order to minimize bias, the survey instruments will include the following design features:

- Response options for multiple-choice questions will be randomized, where appropriate.
- Participants will be asked by the interviewer to answer all questions.

8.6.1. Data handling conventions

Management of survey data will be performed by a CRO in accordance with applicable GSK standards. Personally identifiable information will not be transmitted to GSK, in accordance with GSK policies.

8.6.2. Resourcing needs

This study is overseen by a senior PhD level epidemiologist, MD level physician and GSK Study Accountable Person (SAP). Study management, the reporting analysis plan, data collection, data analysis and reporting will be provided by a CRO.

8.6.3. Timings of Assessment during follow-up

This is a cross-sectional study assessing the proportion of parents/carers and referring HCPs at six months post-treatment with Strimvelis. There will be no follow up.

8.7. Data analysis

There are two distinct analysis populations comprising all (1) Parents/Carers and (2) referring HCPs recruited in the study. Information on response rate will be summarized. For each analysis population, all data from all survey respondents will be analysed and reported as descriptive statistics. Each survey will be analysed for all countries combined.

8.7.1. Essential analysis

A frequency distribution of responses to each question (the number of respondents who give an answer to each question) will be presented. Summary statistics will be prepared describing the proportion of parents/carers and referring HCPs for whom questionnaires were returned relative to the total number of parents/carers and referring HCPs of patients eligible for enrolment into the study.

For the analysis population, the proportion of participants answering each question correctly and incorrectly will be summarized. In case of multiple choice questions, the number and proportion of participants reporting each response will be provided.

For the analysis population, the proportion of correct answers to survey questions overall and by risk category will be summarized.

Table shells are presented in Annex 2.

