8.3.3. Outcome definitions

This study will assess the proportion of parents/carers and referring HCPs at six months post treatment with Strimvelis that understood the possible risks relating to:

Safety concerns (KRM topics):

- 1. Malignancy due to insertional oncogenesis (e.g. leukaemia, myelodysplasia)
- 2. Autoimmunity
- 3. Unsuccessful response to gene therapy
- 4. Pregnancy

Other areas of interest:

- Requirement for long-term monitoring
- Receipt of the patient treatment alert card

The proportion of parents/carers and referring HCPs who acknowledge receipt of routine and additional risk minimization measures (e.g., SmPC/PIL, educational materials, Patient Alert Card) will be assessed as a measure of implementation.

The type of medical specialty and experience of referring HCPs will be summarized.

The primary outcome of these surveys is the proportion of parents/caregivers and referring HCPs that provide correct responses to a series of questions concerning the specific risks associated with Strimvelis.

Sufficient understanding of a key risk message can be assumed if at least 80% or more respondents correctly answer all questions that are included within that particular key risk message [ISPE White Paper 2016].

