2.1.5 If applicable, that there is no a priori hypothesis?				

Comments:			

Section 3: Study design	Yes	No	N/A	Section Number
3.1 Is the study design described? (e.g. cohort, case-control, cross-sectional, new or alternative design)				10.1
3.2 Does the protocol specify whether the study is based on primary, secondary or combined data collection?	\boxtimes			10.3.1
3.3 Does the protocol specify measures of occurrence? (e.g. incidence rate, absolute risk)				10.3.3
3.4 Does the protocol specify measure(s) of association? (e.g. relative risk, odds ratio, excess risk, incidence rate ratio, hazard ratio, number needed to harm (NNH) per year)			\boxtimes	
3.5 Does the protocol describe the approach for the collection and reporting of adverse events/adverse reactions? (e.g. adverse events that will not be collected in case of primary data collection)	\boxtimes			12

Comments:

This is a descriptive study only

Section 4: Source and study populations	Yes	No	N/A	Section Number
4.1 Is the source population described?	\boxtimes			10.2

Section 4: Source and study populations	Yes	No	N/A	Section Number
 4.2 Is the planned study population defined in terms of: 4.2.1 Study time period? 4.2.2 Age and sex? 4.2.3 Country of origin? 4.2.4 Disease/indication? 4.2.5 Duration of follow-up? 4.3 Does the protocol define how the study 				10.2 10.2 10.2 10.2 10.2
population will be sampled from the source population? (e.g. event or inclusion/exclusion criteria)				10.2
Comments:				
Section 5: Exposure definition and measurement	Yes	No	N/A	Section Number
5.1 Does the protocol describe how the study exposure is defined and measured? (e.g. operational details for defining and categorising exposure, measurement of dose and duration of drug exposure)	\boxtimes			10.3.1
5.2 Does the protocol address the validity of the exposure measurement? (e.g. precision, accuracy, use of validation sub-study)				
5.3 Is exposure classified according to time windows? (e.g. current user, former user, non-use)			\boxtimes	
5.4 Is exposure classified based on biological mechanism of action and taking into account the pharmacokinetics and pharmacodynamics of the drug?				
Comments:				
Section 6: Outcome definition and measurement	Yes	No	N/A	Section Number
6.1 Does the protocol specify the primary and secondary (if applicable) outcome(s) to be investigated?				10.3.3
6.2 Does the protocol describe how the outcomes are defined and measured?				10.3.3

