Please answer based on your knowledge of Strimvelis as informed by the Strimvelis Educational Materials, including the product Summary of Product Characteristics (Product Label).
3. Strimvelis is recommended as first-line therapy for any patient affected by ADA-SCID.
Please select one response.
a. True
b. False
c. I don't know
4. Strimvelis is indicated for the treatment of patients with severe combined immunodeficiency due to ADA deficiency, for whom no suitable HLA matched related stem cell donor is available.
Please select one response.
a. True
b. False
c. I don't know
5. Strimvelis is contraindicated in patients with a history of previous gene therapy.
Please select one response.
a. True
b. False

c. I don't know

CONFIDENTIAL

WWEpi Project number: PRJ2678/205881

6. Patients eligible to receive treatment with Strimvelis should have a bone marrow harvest for stem cell back-up at least 3 weeks prior to treatment with Strimvelis. Please select one response. a. True b. False c. I don't know 7. Parents and carers of patients receiving treatment with Strimvelis should be educated on the fact that the patient should not be able to donate blood, organs, tissues, or cells for transplantation. Please select one response. a. True b. False c. I don't know 8. It is recommended that patients treated with Strimvelis are regularly followed up clinically (at least annually). Please select one response. a. True b. False c. I don't know 9. Strimvelis is contraindicated in patients with a current or previous history of leukaemia or myelodysplasia. [KRM 1] Please select one response. a. True b. False

c. I don't know

CONFIDENTIAL

WWEpi Project number: PRJ2678/205881

10. Have you given advice to parents/carers/patients regarding monitoring for signs and symptoms of leukaemia? [KRM1] Please select one response. a. Yes b. No c. I don't know 11. Have you performed blood tests (including red blood cell indices, white blood cell count differential, platelet count, and a routine biochemistry screen) within the first year of a patient's returning from treatment with Strimvelis? [KRM1] Please select one response. a. Yes b. No c. I don't know 12. Regular monitoring for clinical autoimmunity (possibly including tests for auto-antibodies) is recommended. [KRM2] Please select one response. a. True b. False c. I don't know 13. Autoimmunity may be observed during immune reconstitution after gene therapy. [KRM2] Please select one response. a. True b. False

b. No

c. I don't know

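### The 80% rule counts respondents who get every item of a key risk message right, but 8.7.1 and the Table 4 and Table 8 shells specify no such count

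*Protocol*

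**What the plan says.** **Criterion.** Section 8.3.3 words the main outcome per respondent: "The primary outcome of these surveys is the proportion of parents/caregivers and referring HCPs that provide correct responses to a series of questions". It then sets the standard for each KRM: "at least 80% or more respondents correctly answer all questions that are included within that particular key risk message". The unit is the person, and the person counts only if all items of that KRM are right.

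**Size.** Section 8.5 recruits "until 10 referring HCPs and 10 parents/carers have completed their respective surveys", so the standard means at least 8 of 10 in each group.

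**Analysis.** Section 8.7.1 plans response frequencies and two results on correctness. In the first, "the proportion of participants answering each question correctly and incorrectly will be summarized". In the second, "the proportion of correct answers to survey questions overall and by risk category will be summarized". The unit changes from participants to answers, and only the second result is given by risk category.

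**Shells (Annex 2).** Tables 3 and 7 hold response frequencies. Tables 4 and 8 have one row per question and Total rows for blocks of questions, under columns for correct yes, correct no and a percentage. No row is defined as the number of respondents with every item of a block correct. The 80% threshold appears neither in 8.7 and 8.7.1 nor in the shells.

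**The concern.** The standard needs a joint result per person. The planned outputs are marginal results per question and, by risk category, a share of answers. The joint result cannot in general be recovered from either.

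A report that follows 8.7.1 and Annex 2 as written would therefore lack the figure that the protocol uses to judge understanding. The figure nearest to hand for each KRM would be the Total percentage. If that is a pooled share of answers and someone sets it against 80%, it can only flatter the result. A message on malignancy or failure of gene therapy could then be described as understood when the protocol's own standard is not met.

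**Working it through.** **Inputs.** n = 10 per group (8.5). The threshold is 80% of respondents (8.3.3), so 0.80 × 10 = 8. The items per KRM, k, come from the blocks in Annex 2:

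- HCP survey: malignancy 6 (Q6-11 in Table 4) or 3 (Q9-11 in Table 3 and Annex 4), autoimmunity 2 (Q12-13), unsuccessful response 5 (Q14-18), pregnancy 2 (Q19-20).
- Parent/carer survey: malignancy 3 (Q6-8), autoimmunity 2 (Q9-10), unsuccessful response 4 (Q11-14), pregnancy 2 (Q15-16).

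The protocol gives no power or precision figure to reproduce; 10 per group is stated without a derivation.

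**Step 1: direction.** Let A be the number of respondents with all k items correct. Each contributes k correct answers and the others contribute at least 0, so pooled % = (correct answers)/(10k) ≥ A·k/(10k) = A/10. A pooled figure is never below the all-correct proportion, and if A ≥ 8 it is at least 80%. A discrepancy can only favour a pass.

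**Step 2: size at n = 10.** The highest pooled figure with the rule failed has A = 7 and three people missing one item each: (10k − 3)/(10k). A pooled 80% allows 2k wrong answers, so A can be as low as max(0, 10 − 2k). If every item is at 9/10 there are k misses, so A can be as low as 10 − k.

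| k | Highest pooled % with rule failed | Lowest A with pooled ≥ 80% | Lowest A with every item 9/10 |
|---|---|---|---|
| 2 | 17/20 = 85% | 6 | 8 |
| 3 | 27/30 = 90% | 4 | 7 |
| 4 | 37/40 = 92.5% | 2 | 6 |
| 5 | 47/50 = 94% | 0 | 5 |
| 6 | 57/60 = 95% | 0 | 4 |

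An extreme case for the five-item HCP block: each of 10 HCPs misses one item, spread evenly. Every item prints 8/10, the pooled figure is 40/50 = 80%, and A = 0.

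**Step 3: what the item rows can settle.** Any item at 7/10 or lower caps A at 7, so the rule fails. If the items of a KRM have at most two misses in total, at most two people have a miss, so A ≥ 8 and the rule is met; two items both at 9/10 or more is such a case. With no item below 8/10 and three or more misses in total, A can be 7 or less or 8 or more, and the item rows do not decide.

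**Step 4: how often, under an assumption.** The protocol gives no expected correct rate. Assume independent items with a common rate p. Then P(rule met) = P(Bin(10, p^k) ≥ 8) and P(pooled ≥ 80%) = P(Bin(10k, p) ≥ 8k). By Step 1 their difference is the chance that the pooled figure reaches 80% while the rule fails.

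| p | k = 2 | k = 3 | k = 4 | k = 5 | k = 6 |
|---|---|---|---|---|---|
| 0.80 | 0.389 | 0.543 | 0.579 | 0.581 | 0.576 |
| 0.85 | 0.385 | 0.656 | 0.793 | 0.855 | 0.886 |
| 0.90 | 0.249 | 0.511 | 0.710 | 0.838 | 0.914 |
| 0.95 | 0.063 | 0.160 | 0.279 | 0.402 | 0.519 |

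For example, at p = 0.90 and k = 5, P(pooled ≥ 80%) = 0.991 and P(rule met) = 0.152.

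**Step 5: item sets.** Table 4 totals Q6-11 under malignancy, while Table 3 and the tags in Annex 4 start KRM 1 at Q9. If every HCP had Q6-8 right and missed one of Q9-11, the Q6-11 pool would be 50/60 = 83.3%, the Q9-11 pool 20/30 = 66.7%, and A = 0 on either set. In Table 8 the Q11-14 block carries a total labelled Q15-16, and no total is shown for pregnancy.

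**The case against.** The strongest defence is that 8.3.3 already states the respondent-level outcome and rule, that 8.6.2 assigns a reporting analysis plan to a CRO, and that the coded participant-level dataset in 9.2 allows the count at any time. A reader might infer from the mismatch that the rule will never be evaluated. The documents do not support that: the gap is shown only for 8.7.1 and Annex 2, and the reporting analysis plan, which is not at hand, may close it. The point still stands for the protocol, which does not leave the statistic open. It specifies essential analyses and shells that do not match its criterion, and 11.2 ties the final report to the planned analyses described in the protocol.

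A reader might also take it as fact that the Total rows pool answers. No text defines them, and the item rows above them count respondents. Pooling is the reading that 8.7.1 supports, but it is an inference, and the ambiguity itself needs removing.

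Nor can it be said that the protocol plans a false pass. It nowhere compares a Total with 80%, and doing so would contradict 8.3.3. The case of 40/50 against 0/10 is a constructed extreme, and the item rows sometimes settle the rule.

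Finally, the ENCePP checklist in Annex 3 says "This is a descriptive study only", and no test or action is tied to 80%. That limits the consequence. It does not remove the mismatch, because an all-correct count is itself descriptive and section 7 uses the study to help judge whether the measures were successfully implemented.

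**Conclusion.** The concern holds as a mismatch between a stated criterion and the stated analysis. Section 8.3.3 needs the proportion of respondents with every item of a KRM correct; 8.7.1 and the Table 4 and Table 8 shells do not specify it.

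If the Total rows pool answers, at n = 10 a KRM that fails the rule can print up to 85% to 95% for two to six items, and the error can only run towards a pass. These limits are pure counting. The probabilities in Step 4 rest on independent items with an equal correct rate, taken over an assumed range of 0.80 to 0.95; they show that the divergence need not be rare and do not forecast it.

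No data would be lost, so the fault can be fully corrected.

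**What to change.** 1. **Reconcile the item sets first.** Settle whether HCP KRM 1 is Q6-11 or Q9-11 and make Tables 3 and 4 and Annex 4 agree. In Table 8, correct the label on the Q11-14 total and add the pregnancy total. State whether items that ask what was done rather than what is known (HCP Q10-11, parent/carer Q7) are scored. Until this is done the all-correct count for HCP KRM 1 is not defined.
2. **Section 8.7.1.** State that the primary result for each KRM and each group is n/N (%) of respondents with every scored item of that KRM correct, and that this figure is compared with 80%.
3. **Tables 4 and 8.** Add that row for each of the four KRMs. Label the Total rows as pooled item-level percentage correct, supportive and not compared with 80%.

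The cost is minor text and shell edits plus the decisions in step 1, with no new data. The KRM percentages set against 80% may look less favourable than pooled ones, since they can never be higher.

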8.8. Quality control and Quality Assurance

The following measures will be taken to ensure data quality and integrity:

- All procedures will be performed according to the protocol and will be documented appropriately.
- The electronic data capture system will be built to include drop-down lists and select buttons to minimize typing errors by the telephone interviewer as much as possible. The system allows data entry checks to be implemented, as well as complex skip patterns, and other functionalities.

Survey questions will be reviewed by an internal physician (not involved in this project) and by a patient group representative, prior to starting the survey, to ensure readability and understanding of the questions.

8.9. Limitations of the research methods

This study has the following limitations:

- Small sample size: given the rarity of the disease a high response rate is important. The response rate will most likely be dependent on who is willing to participate in the registry. The actual time of survey participation coincides with the follow up regime of the registry and is thus not seen as a major challenge.
- Recall bias: there may be a potential recall bias when answering more complex questions as the educational materials were distributed at least 6 months prior to the telephone interviews (at the time of entering the registry and consenting to both the registry and this survey). Therefore medical terms are often explained before asking a specific question, to ensure understanding of the topic.
- Possible bias due to telephone interviewer led questioning and their delivery style.
- Possible misunderstanding on the part of participants or questionnaire fatigue could lead to inaccurate answers. Therefore, questions have been limited to approximately 20 only and some of the medical terms or themes are introduced before a particular question is asked.
- The participants' educational attainment is unknown; and we assume that participants are representative of the entire Strimvelis HCPs/parents/carers spectrum and that the questions can be understood across the entire educational range.
- Parents/Carers of patients who did not respond to treatment may understandably be under extreme stress with potentially many medical interactions happening unrelated to Strimvelis which may impact their recall of educational materials. Stratification of the survey results by response to treatment may help in discarding this imbalance.

8.10. Study closure/uninterpretability of results

The study will be closed when 10 parents/care givers and 10 HCPs have completed the surveys. The survey will begin with a question indicating the agreement to participate in the survey. If the individual does not agree, the survey will be ended.

Ethics approval will be sought as required by individual countries.

8.11. Other aspects

None

9. PROTECTION OF HUMAN SUBJECTS

To ensure the quality and integrity of research, this study will be conducted under the Guidelines for Good Pharmacovigilance Practices (GVPs) and Good Pharmacoepidemiology Practices (GPPs) issued by the International Society for Pharmacoepidemiology (ISPE) (ISPE, 2008), the Declaration of Helsinki (Declaration of Helsinki, 2008) and its amendments, and any applicable national guidelines.

9.1. Ethical approval and subject consent

The survey participation is voluntary.

Parents/carers being followed within the long-term registry, who have specifically agreed to be contacted for such studies, will be asked to consider and give informed consent for this study of their understanding of educational materials.

HCPs involved in the long term registry will also be asked to provide informed consent for their participation in this survey.

9.2. Subject confidentiality

Each participant's identity will be known only to GTRC, who will help facilitate completion of the surveys. Identification numbers will be assigned and used to identify participants. The dataset used in the analysis of data will contain coded participant identifiers only.

All parties will ensure protection of patients' and participants' personal data and will not include patient or participant names on any study forms, reports, publications, or in any other disclosures, except where required by law. In accordance with local regulations in each of the countries in which the study is implemented, participants will be informed about data handling procedures and asked for their consent. The registry will be conducted in accordance with all applicable patient and participant privacy and data storage requirements. Regulatory authorities or GSK-approved auditors may inspect the data files, which may include personally identifiable information of participants. In all cases, personally identifiable information will not be transmitted to GSK.

10. MANAGEMENT AND REPORTING OF ADVERSE EVENTS/ADVERSE REACTIONS

The reporting of Adverse Events (AE) is not expected or requested during the survey given that answers are closed ended (i.e., there are no free text fields into which the telephone interviewer could enter AE information on the interviewee's behalf). However, as reporting suspected adverse reactions after authorisation of the medicinal product is important to allow continued monitoring of the benefit/risk balance of the medicinal product, physicians will be asked to report any suspected AEs via the national reporting system.

All serious and non-serious adverse events (AEs), pregnancy exposures, or incidents related to any GSK product will be collected and reported as described in the study-specific pharmacovigilance plan (sPVP). This plan will include the following elements to ensure a comprehensive approach to safety event collection and reporting:

- Supplier pharmacovigilance training
- Investigator and site staff pharmacovigilance training
- Safety-specific roles
- AEs, pregnancy exposures, and incidents collection and reporting processes
- AE, pregnancy exposure, and incident collection forms
- Frequency of data review
- Reporting process and timelines
- Interim reports
- Reconciliation process
- Study-specific PVP monitoring process
- Provision of final study report

